15.6 Pregnancy Reporting

If a female participant becomes pregnant within 12 weeks of receiving laser therapy the details of the pregnancy needs to be reported to the Chief Investigator, Trial Manager and Sponsor within 24 hours of the site learning of its occurrence on the pregnancy reporting form.

15.7 Reporting Urgent Safety Measures

An Urgent Safety Measure (USM) is an action that the sponsor or an Investigator may take in order to protect the subjects of a trial against any immediate hazard to their health or safety. Upon implementation of an USM by an Investigator, Newcastle CTU must be notified immediately and details of the USM given. Newcastle CTU must inform the NHS REC within 3 days of the USM taking place in accordance with the sponsor's/NCTU's standard operating procedures.

16. STATISTICAL CONSIDERATIONS

Definitions of outcome measures, scoring procedures and derivations of overall and domain scores for the primary outcome OMWQ-HN score and secondary measures of WHO mucositis score, EORTC QLQ C30 (version 3.0) EORTC H&N 35, EQ-5D 5L (version 1.0) are presented in Appendix 4.

Adverse events are coded according to MEDRA coding with severity coded according to WHO CTC 4.0 grading system.

Survival is defined as date of randomisation to date of death from any cause, survivors censored at their date of last follow-up visit.

Time to recurrence is defined as date of randomisation to date of clinical recurrence for patients with confirmed date of clinical recurrence or patients with confirmed disease related death - survivors who are recurrence-free and patients who have died from other causes are censored at their date of last follow-up visit.

Primary analyses are carried out on an intention to treat, retaining all randomised patients in the analysis according to their randomised treatment allocation, and a complete case basis. Sensitivity analyses may be performed on a per protocol basis, according to treatment received, and on an imputed dataset, should missing data deem this necessary. Treatment related adverse events will be reported in all patients starting treatment.

A full analysis plan will be in place prior to any comparative analyses, and will be reviewed by the oversight committees.

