8.1 Risk Assessment

The laser is being used within the CE (Conformité Européenne) marked indication for reducing pain and inflammation for patients with OM.

Class 3b lasers are potentially harmful to the retina. This hazard can be reduced with the provision of laser glasses from the device manufacturer which must be worn by both the practitioner and the patient whilst the device is in operation. The eye protection can be worn over prescription glasses. The risk of unintended laser irradiation of the eye will also be reduced through the removal and covering of reflective surfaces in the treatment area. The door of the treatment area will be locked and a sign displayed to indicate the use of laser therapy.

Before the treatment starts the operator will ask the patient to report if the light from the laser becomes too hot. If the heat becomes excessive, the laser will be stopped and the probe allowed to cool down.

The laser must not be used over the pregnant uterus, but will only be used in the oral cavity for this trial. Although in line with manufacturer recommendations the laser can be used with caution in pregnant women, women who are known to be pregnant at the time of their treatment, or are planning to become pregnant, will not be eligible to take part in LiTEFORM. Each participating site will follow their standard protocols for (C)RT, which ensure that women of childbearing age are not pregnant whilst undergoing their (C)RT. If a woman is reported to become pregnant during the treatment, LLLT treatment will be stopped immediately. The patient will be followed for the duration of the trial for outcomes unless she withdraws from the trial.

There is some anxiety amongst physicians that if the laser can stimulate healing of normal cells, that it may have a preserving effect on cancer cells. At present the effects of LLLT on tumour behaviour have been inadequately studied. There are a few published in vitro studies. These studies have inconsistent results, which may reflect varying dosimetry and power of the laser. Although there are no case reports of adverse outcomes following LLLT, it remains biologically plausible that LLLT may have an adverse impact on tumour behaviour resulting in poorer outcome and survival. This trial will

aim to address this question by collecting and reporting tumour recurrence and progression during the study period.

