9.2 Secondary Objective(s)

- Determine the effectiveness of LLLT in preventing severe OM during RT or CRT for HNC as measured by WHO mucositis scores.
- Apply evidence derived from the trial to inform NHS guidance in the use of LLLT for managing OM.
- Investigate the short and long term benefits to patients in terms of dependence on feeding tubes, nutritional status, pain control, admission to hospital, treatment interruptions and swallowing function and quality of life.
- Investigate the long term risks of LLLT (survival, recurrence, disease progression).
- Identify barriers and facilitators to implementing LLLT in routine clinical care through a qualitative process evaluation.

Economic evaluation:

- To compare the total costs, of LLLT and sham LLLT measured at 4 and 14 months, calculated by combining data collected from the eCRF, Health Utilisation and Time and Travel Questionnaires with nationally available unit cost data [13].
- To compare quality-adjusted life years (QALYs) derived from the responses to EQ-5D-5L and EORTC QLQ30 measured at baseline, throughout the trial (week 6 and 4 and 14 months).
- To compare the cost-effectiveness measured in terms of the incremental cost per change (improvement) in OMWQ-HN score recorded between baseline and at week 6 of therapy (as detailed in the statistical primary end point).
- To evaluate incremental cost per QALY of LLLT when compared to standard care (from the

perspective of the NHS and personal and social services to participants and families over 14 months)

Qualitative Sub-study:

 To identify barriers and facilitators to recruitment by interviewing patients, interviewing health professionals, observing launch event and site initiation visits, and audio-recording recruitment consultations.

- To feedback to sites regarding barriers and facilitators that have been identified by developing
 a detailed action plan and site specific feedback.
- To understand practitioners' and site experiences of training in and delivering LLLT and the "fit" of LLLT within the treatment pathway.
- To identify barriers and facilitators to wider implementation of trial findings and LLLT.

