9.3 Outcome Measures

9.3.1 Primary outcome measure

Primary Outcome: OMWQ-HN score at week 6 following start of LLLT treatment.

9.3.2 Secondary outcome measures:

- OMWQ-HN and WHO mucositis scores collected at baseline and weekly during weeks 1-6 of treatment.
- Long term reported health related quality of life as measured by EORTC QLQ C30 (version 3.0),
 EORTC QLQ C30/H&N 35 (EORTC QOL Module for Head and Neck Cancer) and the EQ-5D-5L at baseline, week 6, month 4 and month 14, and MDADI at baseline, week 6, month 4 and month 14.
- Nutritional Parameters as measured by Performance Status Scale's (PSS-HN) collected weekly
 at baseline, weeks 1-6, month 4 and month 14. Recording of weekly weight changes from
 baseline during treatment, the quantity of enteral nutrition consumed, number of days of
 feeding tube in situ.
- Changes in swallowing function measured by the timed water swallow test collected at baseline, week 6 of LLLT month 4 and month 14.
- Pain outcomes as measured by use of analgesics/ topical treatment and pain domain of EQ 5D-5L and OMWQ-HN at randomisation and weekly to week 6 during treatment.

 Safety, specifically adverse events attributed to LLLT and clinical complications notably number of days as inpatient hospital admissions and interruptions in CRT treatment (recorded weekly 1-6 during treatment).

• Clinical outcomes specifically patient survival, quality-adjusted survival recurrence and persistence of disease at 14 months.

Economic outcomes:

- Incremental cost per change in OMWQ-HN score recorded between baseline and at week 6 of therapy and incremental cost per QALY over 14 months
- Quality-adjusted life years based upon EQ-5D-5L [14] and EORTC-8D [15] utility scores measured at baseline, week 6 and 4 and 14 months
- Costs associated with treatment (weeks 0-6) will be collected weekly via the eCRFs
 (e.g. adverse events and use of analgesics)
- Health care utilisation based on responses to Health Utilisation Questionnaire administered at 4 and 14 months (assessing: visits to the GP/walk-in clinic/A&E etc.)
- Participant and family costs collected via the Time and Travel Questionnaire administered at 14 months
- Total costs of LLLT and sham LLLT measured at 4 and 14 months, from the perspective of the NHS and personal and social services to participants and families

Qualitative outcomes as identified through:

- Observations of training
- Interviews with health professionals delivering LLLT

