- Performance Status Scale's (PSS-HN)
- Recording of weight (weight/BMI)
- Timed water swallow test
- Health Care Utilisation Questionnaire (including use of primary, secondary and social health care services and time away from usual activities)

Month 14 (+/- 2 weeks) Head and Neck Follow-up assessment (at the standard care visit)

- MDADI
- EORTC QLQ C30 (version 3.0), EORTC QLQ C30/H&N 35 and EQ-5D-5L
- Performance Status Scale's (PSS-HN)
- Timed water swallow test
- Recording of weight (weight/BMI)
- Health Care Utilisation Questionnaire

• Time and travel questionnaire

The following data will also be recorded at month 14:

- Recurrence, disease progression, death
- Feeding tube use (stopping)

Qualitative Sub-study:

- Patient interviews: 1-2 weeks after the recruitment discussion, and at approximately 4 months or 14 months (maximum of 2 interviews per patient).
- Staff interviews: staff may be contacted at any point during the LiteFORM trial
- Audio-recordings: each recruitment/consent discussion with patients for the LiTEFORM trial
- Observations: launch meeting, site initiation visits and all trial training sessions

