16.1 Statistical Analysis Plan

The primary analysis of the primary outcome is a comparison of the OMWQ-HN score at 6 weeks following start of RT (+/- 2 weeks) in the two randomised arms. Mean baseline and 6-week scores will be presented (with 95% CI) as well as the mean difference from baseline score. Transformation may be appropriate for non-normally distributed data. The null hypothesis to be tested is H0: mean 6-week score in patients randomised to LLLT = mean 6-week score in patients randomised to sham LLLT. Randomisation is stratified by known clinical confounders of cancer treatment: 1. planned treatment (radiotherapy alone or chemo-radiotherapy 2. Unilateral or bilateral radiotherapy fields.

The size and significance of any treatment effect will be estimated in a multivariable linear regression model adjusting treatment by the stratification factor. Secondary analyses of the primary outcome will adjust the size and significance of any treatment effect by other important baseline clinical covariates (importance assessed through univariate modelling) using multivariable regression and ANCOVA. Underlying assumptions of the regression models and non-linear continuous covariates will be investigated, reported and addressed. A two-sided 5% level of significance will be used.

A sensitivity analysis may be carried out on an imputed dataset, based on multiple imputation methods, to deal with missing data and will be described in the Statistical Analysis Plan, which will be

finalised prior to any analysis of unblinded data.

Comparison of secondary outcome measures has not been powered. As such, descriptive statistics such as means (sd, 95% CI), medians (inter-quartile ranges, range) will be presented by randomised treatment arm for continuous secondary outcome measures, specifically scores, feeding tube days, inpatient admission days, water swallow times. ITT proportions (95% CI) will be calculated and presented for categorical measures.

Time to event summary statistics will be estimated using the method of Kaplan and Meier, and 3, 6 and 12-month estimates (with 95% CI) reported. Differences between 'survival' distributions will be estimated using the hazard ratio (95%CI), unadjusted and adjusted by stratification factors.

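### Time to recurrence has no place for persistent or progressive disease, and the SAP's 14-month table neither names progression nor clearly keeps patients who died of disease before the visit

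*Protocol*

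**What the plan says.** Protocol section 8.1 raises the safety question: "it remains biologically plausible that LLLT may have an adverse impact on tumour behaviour resulting in poorer outcome and survival". It says the trial will "aim to address this question by collecting and reporting tumour recurrence and progression during the study period". The secondary objectives in section 9.2 list survival, recurrence and disease progression as three separate long-term risks. The clinical outcomes in section 9.3.2 include "recurrence and persistence of disease at 14 months". Section 13.6 has month-14 data collection cover "Recurrence, disease progression, death".

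Section 16 defines two time-to-event variables: all-cause survival and time to recurrence. The second begins "Time to recurrence is defined as date of randomisation to date of clinical recurrence for patients with confirmed date of clinical recurrence or" and adds patients with a confirmed disease-related death. The rest are handled thus: "survivors who are recurrence-free and patients who have died from other causes are censored at their date of last follow-up visit". Section 16.1 plans the analysis by the method of "Kaplan and Meier, and 3, 6 and 12-month estimates (with 95% CI) reported", with hazard ratios unadjusted and adjusted for the stratification factors.

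The SAP keeps the objective on survival, recurrence and progression (1.2.2) but contains no time-to-event analysis. Its disease outcome (2.4.2) is recurrence and persistence at 14 months, collected only from participants who started laser before 6 July 2018 and summarised as counts and percentages by arm (5.2). Sections 3.2 and 5.5 limit each analysis to participants who attended the relevant visit and have evaluable data.

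**The concern.** If laser protected tumour cells during radiotherapy, the most direct sign would be a tumour that fails to clear or that progresses early. Section 12.1 admits patients for primary as well as adjuvant radiotherapy, and primary patients start with tumour in place, so failure to clear is a foreseeable course. An endpoint that recognises only recurrence and disease-related death handles that course badly: such a patient is either censored or falls into no stated class, and stays in the risk set without being able to recur. The comparison is then least sensitive to the harm section 8.1 describes.

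The SAP's replacement table includes persistence but has two gaps of its own. Progression is an objective with no named analysis, and the attendance rule would leave out patients who died of disease before month 14.

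**Working it through.** Neither document gives a recurrence, persistence or progression rate, or any design figure for this endpoint, so there is no planned figure to reproduce. The check is first a reading of the definition, then an illustration on assumed rates.

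**1. Patient courses under section 16**

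- Complete response, recurrence at month 8: event at month 8. Correct.
- Tumour never clears, or progresses at month 4, alive at last visit: neither a recurrence nor a disease-related death. The nearest class is the recurrence-free survivor, so censored.
- Progression at month 3, death from disease at month 10: an event, but with no clear date. If dated at death, it is 10 − 3 = 7 months late.
- Progression, then death from another cause: censored.

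The word recurrence cannot simply be stretched to cover these courses, because sections 8.1, 9.2 and 13.6 list progression beside it and section 9.3.2 lists persistence beside it.

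**2. Direction of the effect (assumed rates)**

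Let r be the 14-month recurrence risk among controlled tumours, p the proportion with persistent or progressive disease, and q the fraction of those who die of disease by month 14.

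- Risk under section 16 = (1 − p)r + pq
- Risk with persistence and progression counted = (1 − p)r + p
- Approximate hazard ratio = ln(1 − laser risk) / ln(1 − sham risk)

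Take r = 20% in both arms, and p = 10% on sham and 20% on laser.

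| q | Sham risk | Laser risk | Approx. HR |
|---|---|---|---|
| 0 | 0.18 | 0.16 | 0.88 |
| 0.3 | 0.21 | 0.22 | 1.05 |
| 0.6 | 0.24 | 0.28 | 1.20 |
| 1 | 0.28 | 0.36 | 1.36 |
| any q, counted as events | 0.28 | 0.36 | 1.36 |

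With p = 5% and 10%, the ratio under section 16 runs from 0.94 (q = 0) to 1.10 (q = 0.6), against 1.20 when these failures count. The definitions give the same event totals only if every such patient dies of disease within follow-up.

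**3. Share of failures missed (assumed rates)**

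Suppose that per 100 patients 10 recur after response and x = 5 to 15 have persistent or progressive disease, half of them alive at month 14. Missed failures are x/2 out of 10 + x: 2.5/15 = 17% to 7.5/25 = 30%. Among the 87 randomised (SAP 2.6), 2.5% to 7.5% is about 2 to 7 patients over both arms, and fewer in the month-14 subset.

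**4. The SAP table (same assumptions)**

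The other x/2 die of disease before month 14 and cannot attend. With no other losses, and living progressors counted as persistent, the table would show:

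- x = 5: (15 − 2.5)/(100 − 2.5) = 12.8%, against a true 15%
- x = 15: (25 − 7.5)/(100 − 7.5) = 18.9%, against a true 25%

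**The case against.** The strongest reply is that the criticised endpoint is not in the SAP. Section 16 defers to a full analysis plan, and that plan replaces time to recurrence with a 14-month table that names persistence. The SAP also works from protocol version 4.0, whereas the protocol available is version 2.1, so the definition may since have changed. This stands, and it limits the practical effect.

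Second, a reader might infer that the protocol expressly censors patients with persistent or progressive disease, and dates their deaths months late. It does not say so. Clinical recurrence is undefined, and the event date for a disease-related death without prior recurrence is not clearly stated. Both are natural readings rather than stated rules, but the wording needs settling either way.

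Third, harm has other routes to notice. Progression is recorded at month 14, survival has its own definition, and section 15.5 sends all deaths to the data monitoring committee. So the trial as a whole is not blind to tumour harm. These routes do not, however, give progression a named comparison between arms in either document.

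Fourth, the figures above are assumptions. The reversed ratio of 0.88 needs persistence to double on laser and no such patient to die of disease by month 14. The secondary outcomes are also unpowered, with no hypothesis tests planned. This stands: the calculation shows direction, not size.

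Fifth, section 13.6 lists disease status only at month 14, so dating persistence or progression needs a search of notes. That is a real cost, though a limited one with 87 patients.

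**Conclusion.** The definition in protocol section 16 is incomplete for the question it serves. It counts neither persistence nor progression and leaves the date of some disease-related deaths open. On the natural reading, an excess of such failures on laser would be diluted in the hazard ratio and the Kaplan-Meier estimates. How far is unknown, because the documents give no rates; the 17% to 30% of failures missed, and the hazard ratios shown, hold only under the stated assumptions.

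The documents do not support the stronger inference that the final analysis hides tumour harm: the SAP drops this endpoint and tabulates persistence. What remains in the SAP is narrower: progression is an objective without a named analysis, and the attendance rule, read literally, removes patients with the worst disease outcome from the 14-month table. The effect on the final report is modest, and the point is worth correcting because the correction is cheap.

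**What to change.** - **Protocol section 16:** define the event as the earliest of recurrence, documented progression, persistent disease or disease-related death. State the event date for each, including a disease-related death with no prior recurrence. Where no assessment is scheduled, take the date from clinical notes.
- **SAP 5.2:** report disease failure by month 14 by arm, as recurrence, persistence or progression, disease-related death, and the composite. The denominator should be all participants who started laser before 6 July 2018. Count those who died before the visit, as a stated exception to the attendance rule in 3.2 and 5.5.

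The cost is a change of wording and one revised table. Recurrence, progression and death are already recorded at month 14, but some dates must be read from notes after the last visit (27 October 2019). Numbers will be small, so the results should stay descriptive.

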16.1 Statistical Analysis Plan

The primary analysis of the primary outcome is a comparison of the OMWQ-HN score at 6 weeks following start of RT (+/- 2 weeks) in the two randomised arms. Mean baseline and 6-week scores will be presented (with 95% CI) as well as the mean difference from baseline score. Transformation may be appropriate for non-normally distributed data. The null hypothesis to be tested is H0: mean 6-week score in patients randomised to LLLT = mean 6-week score in patients randomised to sham LLLT. Randomisation is stratified by known clinical confounders of cancer treatment: 1. planned treatment (radiotherapy alone or chemo-radiotherapy 2. Unilateral or bilateral radiotherapy fields.

The size and significance of any treatment effect will be estimated in a multivariable linear regression model adjusting treatment by the stratification factor. Secondary analyses of the primary outcome will adjust the size and significance of any treatment effect by other important baseline clinical covariates (importance assessed through univariate modelling) using multivariable regression and ANCOVA. Underlying assumptions of the regression models and non-linear continuous covariates will be investigated, reported and addressed. A two-sided 5% level of significance will be used.

A sensitivity analysis may be carried out on an imputed dataset, based on multiple imputation methods, to deal with missing data and will be described in the Statistical Analysis Plan, which will be

finalised prior to any analysis of unblinded data.

Comparison of secondary outcome measures has not been powered. As such, descriptive statistics such as means (sd, 95% CI), medians (inter-quartile ranges, range) will be presented by randomised treatment arm for continuous secondary outcome measures, specifically scores, feeding tube days, inpatient admission days, water swallow times. ITT proportions (95% CI) will be calculated and presented for categorical measures.

Time to event summary statistics will be estimated using the method of Kaplan and Meier, and 3, 6 and 12-month estimates (with 95% CI) reported. Differences between 'survival' distributions will be estimated using the hazard ratio (95%CI), unadjusted and adjusted by stratification factors.

Quality adjusted survival analyses will be carried out to simultaneously assess quality and survival functions. A Quality function, based on the EQ5D global score, will be estimated at each survival event time using interpolation, and the survival distribution down-weighted by any negative quality function. The area under each of the survival and quality adjusted survival curves will be presented as (with 95%CI).

Long term data will be presented graphically including proportions of positive and negative changes from baseline. Standardised area under the curve analysis will be used to describe longitudinal quality of life scores. Exploratory, descriptive hierarchical modelling, not based on significance testing, may be used to explore repeated measures nested within patients accounting for important baseline clinical confounders and stratification factors.

Hypothesis testing is not planned for the analyses of secondary outcome measures.

